5.1.1 Study Date Range and Duration

There is a pressing need to begin this study as soon as possible due to the US health and economic crisis. We are ready to begin the clinical trial immediately after the IRB is approved as all the material needed for the test is in hand.

Namely, all the initial materials to begin the study are in hand, including the smell device card, bags, and golf pencils. In discussion with CT **[name]** whom represents Fairfield County (Greenwich & North Stamford) Greenwich Hospital (a Yale New Haven Health System affiliate) was identified as a good site for the drive through outpatient testing. Yale New Haven Hospital is also an ideal site given the volume of testing. The Nursing home of Waveny Life Care in New Canaan as an appropriate site for asymptomatic subjects, for they have done widescale PCR screening and they have at least 30 asymptomatic COVID+ people and staff. The President and CEO of Waveny (**[name], MPA/MHA, FACHE**) is eager to begin as soon as possible and will complete PCR tests of all subjects and provide nurses to assist with administration of the test. They also have ~250 untested employees and thus have a young high-risk cohort and would be eager to test asymptomatics. We expect that the initial testing will be done in < 2 weeks (depending on the local incidence rate), with all completed studies taking as little as 3 weeks, with a maximum estimated duration of ~6 weeks. These studies could begin almost immediately after approval from Yale's IRB.

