5.3.2 Eligibility Criteria/Vulnerable Populations

Inclusion: In order to be eligible to participate in this study, an individual must meet all of the following criteria:

1. Provision of signed and dated informed consent form
2. Stated willingness to comply with all study procedures and availability for the duration of the study
3. Male or female, aged 18 or greater
4. Have a corresponding PCR test for SARS-CoV-2 on the same day.

Exclusion: An individual who meets any of the following criteria in either study population will be excluded from participation in this study (as this may cause unnecessary risk to the test subject or confound the results if the subject has pre-existing anosmia).

1. Adults unable to consent
2. Individuals who are not yet adults (infants, children, teenagers)
3. Pregnant women
4. Individuals with allergic to fragrances
5. Asthmatics

6. Patients with known neurocognitive disorders: dementia, Alzheimer's disease, Parkinson's disease
7. Adults with Acute or Chronic rhinosinusitis (They will be asked if they have a 'stuffy or runny nose'; they may be included in some tests, but their analysis would be segregated as they may be false positives due to allergies or a common cold or flu)

6 Methods

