6.3 Study Procedures

For the outpatient drive-up studies the following protocol steps will be performed.

1. As patients drive-up and are still in the car with the windows closed a HCW with suitable PPE will place a ziplock pouch under the wiper of the driver's side windshield. The bag will contain the following materials:
 - a. A consent form
 - b. A pre-sharpened 'golf-pencil'
 - c. The 'u-Smell-it' olfactory device test card
 - d. A multiple choice answer form
2. While in the car, if the patient consents, they will sign the consent form, read the simple instructions (which are also shown as pictograms to make it very easy to follow), take the test, and fill in the answers. This process will take about 1 minute.
 - a. Description of the test: The test card device has 5 windows each printed with a different scent (or no scent) and marked #1, 2, 3, 4, and 5. The test subject merely needs to use their pencil to scratch back and forth 3 times the first window, sniff the window, and looking at the answer score sheet pick the best choice of five choices and fill in the multiple choice circle ("no scent", and scent A, B, C or D). For instance this could be: no scent / apple / orange /

cherry /banana / rose. This procedure will be repeated for each of the 5 windows.

- b. The subject will also be asked on the test if:
 - i. "Do you have any new loss of taste or smell?" (Yes/No)
 - ii. "Does anything smell different in the last year?" (Yes/No)
 - iii. Do you have a stuffy or runny nose? (Yes/No)
- c. If the test site is not part of EPIC the patient will be asked their gender and age band (18-29, 30-39, 40-49, 50-59, 60-69, 70-79, 80+)

3. After the patient completes the test they will pull out the **Consent and Multiple choice questionnaire form**, and with the window still CLOSED hold it up to the driver's side window and it will then be photographed by the attending HCW (likely an ENT resident doctor) whom will add the unique identifier number and add it to the EPIC system.

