 - a. [Alternative should there be any issues with the camera or the patient must get out of the car]: The patient will take the completed test packet, place it back in the pouch and under the windshield. The HCW will take the packet and remove the **Consent Form** and **Multiple choice questionnaire form**, check if it is completed (if ask the patient), and place all remaining materials in a biohazard box for destruction. The Consent form and the Questionnaire will be digitalized (scan or photographed) and linked with EPIC so as to be compared to the PCR test results.
4. Information from the uploaded and **Multiple choice questionnaire form** will be entered by a person authorized to access the information into a table that includes:
 - a. Unique identifier
 - b. Gender
 - c. Age band (10 year)
 - d. Y/N to patient self-identified new loss of smell or taste
 - e. Y/N to patient response to "things in the last year smell different"
 - f. Y/N to patient self-identified blocked or stuff nose
 - g. Individual answers on the 5 window smell test
 - h. RT-PCR results for SARS-CoV-2 (+, - or Inconclusive)
 - i. Any other tests for COVID19 (CT or Serological) if given
5. The data will be analyzed in the following fashion:
 - a. Patients that report a blocked or stuffy nose will be excluded from the main analysis (as COVID-19 loss of smell is not due to nasal congestion); but will be analyzed separately to see how this would confound any interpretation.
 - b. Patients that are denoted SARS-CoV-2 "inconclusive" will be excluded from the main analysis; but will be separately analyzed to see if they colocalize with normosmia or anosmia.
 - c. Patients will be split into SARS-CoV-2 positive and negative. As the negative pool is likely to be much larger it will be statistically matched by gender and age profile (potentially with larger bands – e.g. 20 year, depending on the sample size)

- d. The + and - SARS-CoV-2 groups individual performance on the smell test (score 0-5) will be plotted as a histogram. A cutoff will best be chosen to segregate people with normosmia and anosmia (e.g. score = 2 or 3).
- e. False Positives (FP) and False Negatives (FN) will be identified and used to measure the selectivity and sensitivity, respectfully.
- f. Based on the statistical performance (see Table 1) we will determine when we have enough patients to complete the study with a given value of precision.

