- g. If a subject fails the smell test (hyposmia or anosmia) but is SARS-CoV-2 negative, yet has other symptoms suggesting being positive for COVID19, we will consider re-testing the subject in 2-3 days by the PCR or serological assay in case the loss of smell precedes a PCR result, or the loss of smell extends past the point in which the viral titer is low and no longer picked up by PCR and would instead be detected by an antibody.

6. The treatment of asymptomatic people will follow an identical protocol with the following differences:
 - a. The study group would consist of high risk subjects that are determined to be positive to SARS-CoV-2 (yet asymptomatic) and the control group would be SARS-CoV-2 negative subject of matching age and gender.
 - b. The smell kit will be directly given to the subject and for HCW the test can be performed at their home.
 - c. There will be a variation of the test in which the order of the scents is altered so that the HCW subject can be re-tested.
 - d. The initial sample size is smaller as this study would firstly see if there was a significant increase of the fraction of anosmia or hyposmia subjects in COVID19+ asymptomatic individuals.

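### Earlier SARS-CoV-2 infection is not recorded, so recovered people with lingering smell loss can become PCR-negative controls and dilute the asymptomatic contrast by an unknown amount

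*Combined protocol and SAP*

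**What the plan says.** **Who is a control.** In the asymptomatic cohort, "the control group would be SARS-CoV-2 negative subject of matching age and gender" (Section 6.3, step 6a). In the outpatient cohort the PCR-negative pool is expected to be the larger one, and "it will be statistically matched by gender and age profile" (step 5c). The only infection-status criterion at entry is inclusion 4 in Section 5.3.2: "Have a corresponding PCR test for SARS-CoV-2 on the same day".

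**What the plan says about timing.** Step 5g deals with a person who fails the smell test with a negative PCR. One explanation it offers is that "the loss of smell extends past the point in which the viral titer is low and no longer picked up by PCR". Its remedy covers someone who fails, is negative, "yet has other symptoms suggesting being positive for COVID19, we will consider re-testing the subject in 2-3 days by the PCR or serological assay". No rule says how a re-tested person is then classified.

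**What is recorded.** The form (step 2b) asks about new loss of taste or smell, about nasal congestion, and "Does anything smell different in the last year". The data table (step 4) adds "Any other tests for COVID19 (CT or Serological) if given". Neither asks about an earlier positive test or illness, and the numbered exclusions in Section 5.3.2 do not mention it. Section 7.3 limits record review to age, gender and the COVID test result.

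**Setting.** Section 5.1 gives significant incidence and ongoing PCR testing among the reasons for choosing the sites. Of one nursing home, Section 5.1.1 says "they have done widescale PCR screening and they have at least 30 asymptomatic COVID+ people and staff".

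**Decision.** Section 7.14 allows the asymptomatic part to be discontinued if positives and negatives do not differ in olfactory performance.

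**The concern.** A negative PCR today does not separate someone never infected from someone who has recovered. The plan accepts that the recovered person may still smell poorly. If such people are counted as controls, the background failure rate rises and the difference that step 6d looks for shrinks.

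The existing safeguards do not close the gap in the asymptomatic cohort:

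- Step 5g is optional and requires other symptoms, which asymptomatic controls ordinarily do not have.
- Serology is noted only if it happens to exist, and no analysis uses it.
- The question about smell over the past year is not tied to COVID-19 and has no stated use.
- The exclusion of pre-existing anosmia (Sections 5.1 and 5.3) relies on self-report, while Sections 2.2 and 6.1.1 argue that people underestimate their loss. It is also absent from the numbered list in Section 5.3.2.

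At stake is a false impression of no difference in the arm that can be dropped on that result. The history has to be asked for at the time, because Section 7.5 says the data will be de-identified and de-linked.

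**Working it through.** **1. The plan's own figure.** Table 1 gives widths of 95% intervals. Exact (Clopper-Pearson) intervals reproduce the worked examples: 90/100 gives 0.824 to 0.951 (width 0.127, table 0.13) and 360/400 gives 0.866 to 0.928 (width 0.061, table 0.06). They match 34 of the 35 cells; the exception, 0.60 at n = 250, is 0.1248 against 0.13. Table 1 is sound, but it covers precision only. The documents give no power or effect size for the asymptomatic contrast.

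**2. Inputs.** Group size of about 100 positives and a similar number of negatives is from Section 5.3.1; Sections 6.4.2 and 6.4.3.2 instead give up to, or about, 250 health care workers in total. Everything else is assumed:

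- f = share of controls who have recovered from infection
- r = share of recovered controls who fail the smell test
- p0 = failure rate in other controls, 10%
- p1 = failure rate in asymptomatic positives, 25%
- two-sided alpha 0.05

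**3. Effect on the contrast.** The observed control failure rate is p0* = (1 − f) × p0 + f × r, a shift of f × (r − p0). The shift is zero when r = p0.

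- f = 10%, r = 25%: 0.9 × 0.10 + 0.1 × 0.25 = 0.115
- f = 10%, r = 50%: 0.9 × 0.10 + 0.1 × 0.50 = 0.140

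Power = Φ[(d − 1.96 × SE0) / SE1], with d = p1 − p0*, m the mean of the two rates, SE0 = √(2m(1 − m)/100) and SE1 = √(p1(1 − p1)/100 + p0*(1 − p0*)/100).

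| Controls | p0* | d | SE0 | SE1 | Power |
|---|---|---|---|---|---|
| none recovered | 0.100 | 0.150 | 0.0537 | 0.0527 | 80.2% |
| f 10%, r 25% | 0.115 | 0.135 | 0.0546 | 0.0538 | 69.8% |
| f 10%, r 50% | 0.140 | 0.110 | 0.0560 | 0.0555 | 50.1% |

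With an assumed split of 30 positives and 220 negatives (250 in total), the unequal-group form of the same formula gives 62.9%, 53.0% and 37.0%.

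**4. Effect on observed specificity.** With specificity Sp in the other controls, observed specificity = (1 − f) × Sp + f × (1 − r).

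- Sp = 95%, f = 10%, r = 30%: 0.855 + 0.070 = 92.5%
- Sp = 95%, f = 20%, r = 30%: 0.760 + 0.140 = 90.0%
- Sp = 90%, f = 10%, r = 50%: 0.810 + 0.050 = 86.0%

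For scale, at Sp = 90% and r = 50% the drop equals the exact 95% half-width when f = 0.0636/0.40 = 15.9% with 100 negatives, or 0.0356/0.40 = 8.9% with 300.

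**5. What setting these people aside costs.** If all recovered controls are identified and f = 10%, the contrast is 100 against 90. Then m = (25 + 9)/190 = 0.179, SE0 = √(0.179 × 0.821 × (1/100 + 1/90)) = 0.0557, SE1 = √(0.001875 + 0.001) = 0.0536, and power is Φ[(0.150 − 0.1092)/0.0536] = 77.7%. For specificity at 90%, going from 300 to 270 negatives widens the interval from 0.071 to 0.075.

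**The case against.** **Specificity.** A reader might infer that specificity is biased downward. The documents do not support that. Section 4.2 defines the target as infection identified by PCR, and Section 3.2 describes a pre-screen that PCR would confirm or refute. Against that target, a recovered PCR-negative person who fails the card is a genuine false positive. Specificity is lower, but it is the specificity the device would have in use, and removing these people from the main figure would flatter it. This objection stands. It does not rescue the asymptomatic contrast, which asks whether current infection carries smell loss.

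**Size of f.** A reader might set the 30 known positives against about 100 controls and take f to be as high as 30%. That does not follow. The 30 come from one home and include residents, while Sections 6.4.2 and 6.4.3.2 describe the cohort as health care workers, drawn from several homes and numbering up to 250. Section 6.3.3 says asymptomatic positives would already be identified by the facility, so the 30 may be meant as cases. Section 5.1.1 also describes about 250 employees there as untested. The documents give no basis for any particular f.

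**Duration.** Section 3.2 posits a transitory loss of about 7 days, and one self-report survey in Section 2.2 gives a mean recovery of 7 days. If smell returns before or together with a negative PCR, r is close to p0 and the effect is close to nil. This stands as a limit on size. The documents do not say how long PCR stays positive, and step 5g treats persistence beyond it as a real possibility.

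**Weight.** The arm is described as more exploratory, Section 7.14 is permissive, and Section 6.4.4 concedes that PCR error may make the test look worse. That section does not mention past infection and plans no sensitivity analysis.

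**Conclusion.** The point holds in a limited form. Past infection is not ascertained, the plan's own reasoning makes it relevant, and step 5g ordinarily cannot reach asymptomatic controls. The direction is toward no difference whenever recovered controls fail more often than the others. The size cannot be determined from the documents: it runs from nothing (r = p0) to, in the scenarios above, a fall in power from about 80% to 70% or 50%. Those figures rest on assumed failure rates, f, r and alpha. Specificity against PCR status would be lower rather than biased. This is a worthwhile, inexpensive improvement to an exploratory comparison; it does not invalidate the primary analysis.

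**What to change.** Add one item to the form and one field to the step 4 table: *Positive COVID-19 test before today? Yes/No, month*. At the nursing homes, fill it from the facility's existing screening list where available, and supplement it with any serology already recorded under step 4i.

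Report the asymptomatic contrast and the specificity twice: with all PCR-negative controls, and without those previously positive or seropositive. Keep all PCR-negative subjects as the primary denominator for specificity. Have both versions of the contrast in view before Section 7.14 is applied.

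The cost is one question, one column, one extra results row and slightly fewer controls in the restricted analysis. Use of the facility list also needs a matching line in Section 7.3. Undiagnosed past infections, for example among untested staff, would still be missed, so the change reduces the problem without removing it.

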- Waveny LifeCare Nursing Home in New Canaan, CT
 - Point Pleasant Nursing Home, Bradenton, Florida
 - Westminster Winter Park/Baldwin Park Nursing Home

Primary Outcome Variables

The subject's score on using the olfactory device will be compared to the PCR results

(SARS-CoV-2 negative or positive) on COVID19 outpatients. As the smell test has a variable scale (0-5) the ideal cutoff will be determined to maximize these factors:

- Sensitivity
- Specificity
- Accuracy

The score with the olfactory device will also be compared to subjects' response to the question "Do you have a new loss of smell or taste?" (current standard). Repeatability will also be examined in a test-retest score conducted within 24 hours with a second device in which the sequence of the odorants is altered.

Secondary and Exploratory Outcome Variables (if applicable)

We will determine if 'asymptomatic' SARS-CoV-2 positive subjects experience a partial loss of smell (hyposmia) and if so determine the fraction of subjects in which this occurs. Sensitivity, specificity and accuracy will be measured.

Visit Schedule Table (Optional). N.A.

Study Flow Chart (optional). N.A.

Abbreviations

Abbreviation	Explanation
HCW	Health Care Worker
UPSiT	University of Pennsylvania Smell Identification Test
COVID-19- or COVID-19+	Negative for COVID-19 virus (as determined by RT-PCR) or Positive for COVID-19 virus (as determined by RT-PCR)
ICU	Intensive Care Unit
IFRA	International Fragrance Association
CPSIA	Consumer Product Safety Information Act

Glossary of Terms

Glossary	Explanation
Anosmia	Full loss of ability to smell odors
Hyposmia (aka. Microsmia)	Partial loss of ability to smell odors
Normosmia	Normal olfactory function and ability to smell odors (most people)
COVID-19	Disease associated with the SARS-CoV-2 coronavirus

Table of Contents

Synopsis.....	3
Primary Objective	3
Secondary Objectives (if applicable)	3
Study Duration.....	3
Study Design	3
Study Population	3
Number of Participants.....	4
Number of Study Sites	4
Primary Outcome Variables	4
Secondary and Exploratory Outcome Variables (if applicable).....	4
Visit Schedule Table (Optional)	4
Study Flow Chart (optional)	4
Abbreviations	5
Glossary of Terms.....	6
1 Introduction	10
1.1 Introductory Statement.....	10
2 Background.....	11
2.1.1 Device Preclinical Experience	11
2.1.2 Device Clinical Experience	11
2.2 Background/prevalence of research topic	11
3 Rationale/Significance	13
3.1 Problem Statement	13

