2.1.1 Device Preclinical Experience

A common assay to detect anosmia (loss of smell) is the use of 'scratch-n-sniff™' type of scent cards, as in the long establish University of Pennsylvania SIT (UPSIT) olfactory test (Doty et al, Laryngoscope, 1984, 94, 176-8). Here microencapsulated non-toxic scents are scratched by the test subject, sniffed and in a discriminatory forced-choice manner the subject chooses the best matching scent choice as part of a multiple choice exam. Typically this is a long format taking 10-15 minutes and is optimized to minimize malingering. There are also shorter format tests. This UPSIT type of test is recognized by the FDA for general anosmia and in the field of use of neurological diseases (e.g. Parkinson's and Alzheimer's Disease). However, the UPSIT test is long, expensive and non-variable, neither of which makes it suitable for widespread or repeated testing. [name] designed and had manufactured a new design of olfactory test card (*u-Smell-it™*) that could be deployed widespread. These 'scratch and sniff'™ type devices are deemed safe by the FDA as they are non-invasive and use non-toxic fragrance. The device card proposed here uses the same fragrance and microencapsulation process as used in the NIH Toolbox® tests for loss of smell. Further the fragrances used in the *u-Smell-it™* test kit are compliant with IFRA and its components do not contain oils derived from nuts, wheat or glutens and do not use any phthalates or their derivatives. These formulations are in widespread use in children's books and cards for over 40 years, as well as other consumer markets. Further, the FDA has approved of use of a 'scratch-n-sniff™' for anosmia. As described below there is now strong mounting evidence for the association of anosmia and COVID-19, albeit largely through patient surveys (see Background 2.2).

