5.2 Outcome Variables

5.2.1 Primary Outcome Variables

The subject's score on using the olfactory device will be compared to the PCR results (**SARS-CoV-2 negative or positive**) on COVID19 outpatients. As the '*u-Smell it*' test has a variable scale (0-5) the ideal cutoff will be determined to maximize any one (or combination) of these factors:

- Sensitivity

- Specificity
- Accuracy

We will compare the performance of the smell test to the current CDC metric of self-described assessment of smell loss (the de facto standard – e.g. “I have a new loss of smell or taste”) in terms of sensitivity, specificity and accuracy. Repeatability will also be examined in a test-retest score conducted within 24 hours in a random subset of 25 asymptomatic HCW with a second device in which the order of the odorants is altered.

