6.1 Treatment – Device

6.1.1 Intended Use for Device

The intended use of the ‘u-Smell-it’™ olfactory test device is to in a quantitative, fast and repeated manner rapidly determine if an individual has a loss of smell and if so, based on the score and the precision of the device determine the likelihood that s/he is at risk of being positive for SARS-CoV-2. This result would in turn serve as a quantitative indicator to guide judicious action (analogous to how temperature is used to truly identify a fever vs. patient self-identification) – e.g. a follow up PCR test. The comparative gold standard (most used) is the question of if the person believes that s/he has “a new loss of smell or taste”, as currently stipulated by the CDC (whether performed in a written or electronic questionnaire). While there are other smell based test kits they are either very long (10-15 min) and tedious (UPSIT) and will not be suitable for wide-scale rapid testing, or for the rapid 3-item SIT are non-variable, and as such will not be a blinded test, especially for repeated testing. Thus, we will compare the performance of our *u-Smell-it* test to the user-identified stated “new loss of smell/taste” – and anticipate a real unbiased test to greatly outperform a highly subjective assessment. A related underlying hypothesis that we seek to test in this trial is that COVID19+ people perform poorly in self-assessments and grossly underestimate their loss of smell. If this premise is validated AND the performance of the device is statistically high (especially in terms of sensitivity) then one would seek FDA approval under emergency authorization use (EUA). If this eventually clears the FDA then it would be used in wide scale US testing at the state and federal level.

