6.1.2 Device Administration and Schedule

The device requires minimal preparation. The only key aspect is to not inadvertently damage it and as such would be given in a sealed pouch with a ‘golf pencil’, consent form, instructions and multiple choice answer sheet.

Patients who are in queue for drive-through COVID-19 testing will be approached by a research team member. No prior medical information will be provided to the study team regarding a patient’s eligibility.

The device in a pouch would be given to drive up outpatients that are undergoing PCR testing for COVID. Typically, the device packet would be placed on the test subject’s windshield just as they drive in and are waiting. If the subject consents to take the test, it will only take a minute. They will have the smell test and consent form digitally recorded (by camera) as they hold the test answers against the closed windows while inside the car. They will then give a nasal or oral sample for PCR testing, which is not conducted as part of the study. Of note, the subjects are already undergoing PCR testing and the smell study merely piggybacks on this other scheduled test. Thus there is practically no extra burden.

For the asymptomatic test the same protocol will be used, with the only minor difference is that the test can be replicated multiple times with different variants. As these tests are done in presence of a HCW there is little issue of compliance.

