6.4.3 Planned Analysis

6.4.3.1 Primary Analyses

Loss of smell in outpatients will be compared to the presence of SARS-CoV-2 coronavirus, as determined by RT-PCR. Key metrics that will be statically evaluated and done with support of YCCI and Yale biostatisticians Profs. [name] and/or [name] Sensitivity are:

- Sensitivity
- Specificity
- Accuracy
- Repeatability

- Other parameters that will be considered are the Area under the Curve (AUC)

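### The altered-order card is described only for the retest, so in the 25 repeat tests card version cannot be separated from practice or occasion; randomising the card order would separate them with no extra subjects.

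*Combined protocol and SAP*

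**What the plan says.** All references are to the combined protocol and SAP.

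- **Synopsis, Primary Outcome Variables:** repeatability comes from a "test-retest score conducted within 24 hours with a second device in which the sequence of the odorants is altered".
- **Section 5.2.1:** the retest is done "in a random subset of 25 asymptomatic HCW with a second device in which the order of the odorants is altered".
- **Section 6.3, step 6c:** for the asymptomatic cohort there is "a variation of the test in which the order of the scents is altered so that the HCW subject can be re-tested".
- **Section 6.1.2:** for asymptomatic subjects "the test can be replicated multiple times with different variants". The plural suggests more than one variant, but it concerns replication, not the first test.
- **Section 6.3, step 4:** nine items (a to i) are tabulated per subject: identifier, gender, age band, three yes/no answers, the answer for each window, PCR result and other COVID-19 tests. Card version is not among them, and the differences listed for asymptomatic subjects in step 6 do not add it.
- **Section 6.4.3.1:** "Repeatability" is listed among the key metrics, with no statistic, target or precision.
- **Section 6.4.3.2:** the asymptomatic analysis also looks for acute smell loss in short longitudinal testing.

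No section randomises or counterbalances which card comes first.

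**The concern.** The two tests differ in two ways at once. The second card has another scent order, which may be easier or harder (for instance through adaptation to the preceding scent). It is also a second attempt within 24 hours, at a task the subject now knows. If everyone goes from standard to altered, a mean change has two possible sources, and the data cannot say which is at work or whether they offset each other.

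Two uses of the retest suffer. A systematic shift in the repeatability data could not be attributed to the cards or to practice. In the longitudinal question, a harder altered card would look like new smell loss, while an easier card or a practice gain could hide a real one. The score runs only from 0 to 5 and the example cutoffs in 6.3, step 5d, are 2 or 3, so a small shift can move subjects across the line.

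**Working it through.** **The plan's own figures.** The documents give no precision for repeatability. Their only precision calculation is for sensitivity and specificity: a 95% interval of 82 to 95% for 90% sensitivity in 100 subjects (6.4.2). An exact Clopper-Pearson interval for 90/100 is 82.4 to 95.1%, so that figure reproduces. It is not affected by this point.

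**Inputs.** The number retested is 25 (5.2.1). The SD of the within-person score difference is not in the documents; I assume 0.5, 1.0 and 1.5 points to show a range.

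**What each design estimates.** Let v be the version effect (altered minus standard) and o the occasion effect (second test minus first).

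- Standard then altered: mean change = o + v.
- Altered then standard: mean change = o − v.
- Fixed order supplies only the first line, hence only the sum.
- With both orders, the half-sum of the two means is o and the half-difference is v.

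| True o | True v | Fixed order shows | Both orders show (o, v) |
|---|---|---|---|
| 0.5 | 0 | 0.5 | 0.5, 0 |
| 0 | 0.5 | 0.5 | 0, 0.5 |
| 0.25 | 0.25 | 0.5 | 0.25, 0.25 |
| 0.5 | −0.5 | 0 | 0.5, −0.5 |

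The first three cases cannot be told apart under fixed order. The fourth looks like no systematic change.

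**Precision.**

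- Fixed order: SE(o + v) = SD/√25.
- Two orders, 12 and 13 subjects: SE of each effect = (SD/2) × √(1/12 + 1/13) = 0.2002 × SD.

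| Assumed SD | SE, fixed order (sum only) | SE, two orders (each effect) | Approx. 95% half-width (1.96 × SE) |
|---|---|---|---|
| 0.5 | 0.10 | 0.10 | 0.20 |
| 1.0 | 0.20 | 0.20 | 0.39 |
| 1.5 | 0.30 | 0.30 | 0.59 |

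The separation costs no precision and no subjects.

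**What it assumes.** The occasion effect must be the same in both orders (no differential carry-over). If it is o₁ in one order and o₂ in the other, the half-difference becomes v + (o₁ − o₂)/2, so the version estimate is off by half the discrepancy.

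**What 25 subjects can show about agreement.** Exact 95% intervals for the proportion classified alike on both tests: 20/25 gives 59 to 93%, 22/25 gives 69 to 97%, and 25/25 gives 86 to 100%.

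**The case against.** The best defence is that a different card on a later occasion resembles intended repeated use, so the total change is itself of interest. The retest involves 25 subjects in a cohort the plan calls exploratory. The primary accuracy analysis is in outpatients tested once, and retesting does not touch it. All of this stands, and it is why the point is minor. It does not remove the confounding.

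The remedy is also modest. At an assumed SD of 0.8 the SE is 0.8 × 0.2002 = 0.160, so an effect of 0.3 is about 1.9 SE and power is a little under 50%. Two scoring keys bring some risk of scoring a card with the wrong one, which could make a normal result look like smell loss. Both points are fair.

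A reader might also draw stronger conclusions that the documents do not support:

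- **One answer key for every first test, open to sharing among coworkers.** First-test version is unspecified, not stated to be single. Nothing describes answer sharing. The sections also disagree on setting: with a HCW present (6.1.2), at home (6.3, step 6b), or self-performed at the nursing home (6.3.1). These should be reconciled.
- **The device repeats the weakness it criticises.** Section 6.1.1 says that rapid rival tests "are non-variable, and as such will not be a blinded test, especially for repeated testing", and 2.1.1 makes a similar remark about UPSIT. An altered retest card does address recall of one's own first answers.
- **Offsetting effects would be reported as perfect agreement.** Zero mean change is not agreement. At an SD of 0.8, with normal changes rounded to whole points, only about 47% of subjects would keep the same score (|z| < 0.5/0.8 = 0.625).
- **The altered card brings in chance error.** Guessing affects any retest, and counterbalancing does not remove it.

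**Conclusion.** The point holds as a minor design improvement. As described, with the altered card second and no version field, version and occasion effects in the 25 retests are fully confounded. That limits what can be said about repeatability and about short-term change in the asymptomatic cohort. How large either effect is cannot be learned from the documents. Two randomised orders would estimate each with an SE of about 0.10 to 0.30 points for an assumed SD of 0.5 to 1.5, provided there is no differential carry-over. These are rough estimates: they could reveal a large version effect but not establish interchangeability. Table 1, the sample size and the primary outpatient analysis are unaffected.

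**What to change.** In 5.2.1 and 6.3, step 6c, randomise the 25 retest subjects to standard-then-altered or altered-then-standard, about 12 and 13. Add card version and test number to the fields in 6.3, step 4, and score each card with its own key.

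In 6.4.3.1, name the within-person agreement statistic. Report it together with the version and occasion effects and their 95% confidence intervals, taking the SD of the change within each order. State the assumption of no differential carry-over, and state that 25 subjects allow only rough estimates and no claim that the versions are interchangeable. Say also which card version is used at the first test.

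The cost is small: the altered card is already planned and no subjects are added. The downside is managing two keys. Because answers are photographed and entered by hand (7.5), a version mark on each answer form and a check of the key at entry would limit mis-scoring.
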